6.3 Per Protocol Set

If the PPS differs from the FAS by more than 15%, the analyses will be replicated on the PPS. If the PPS and the FAS do not differ by more than 15%, analysis may not be done on the PPS. Final judgments will be made at the blind data review meeting in accordance with ICH E9.

6.4 Adjustments for multiplicity

Multiplicity of the primary efficacy analyses is controlled by using a conditional sequence of hypotheses. The study will be considered to demonstrate statistical significance if the primary analysis has a resulting p-value less than 0.049 for both primary endpoints for both A-study and B-study. No other adjustment for multiplicity is required.

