1.1.3 Clinical Studies

The azeliragon clinical development program to date consists of eight Phase 1 studies in the USA, three Phase 2 studies in North America (US and Canada), two Phase 3 studies (operationally conducted under one protocol) and an open-label extension study conducted globally, described in the Investigator's Brochure.

vTv recently completed two Phase 3 studies (under protocol TTP488-301, STEADFAST A-Study and STEADFAST B-Study) examining the effect of azeliragon on both cognitive (i.e., ADAS-cog11) and functional (i.e., CDR-sb) outcomes in patients with mild dementia of the Alzheimer's disease type. The trial was a randomized, double-blind, placebo-controlled trial in 880 participants with probable mild AD, MMSE 21-26 at screening, CDR 0.5 or 1, receiving stable standard of care (acetylcholinesterase inhibitor and/or memantine) evaluating the efficacy and safety of 18 months of treatment with azeliragon 5 mg/day relative to placebo. The clinical trial design included two separate, identical studies (A-Study and B-Study) operationally conducted under a single protocol. Each study was independently powered to evaluate efficacy with respect to co-primary endpoints of ADAS cog11 and CDR-sb and were randomized separately. Patients were randomized 1:1 (site-based randomization) to azeliragon (5 mg/day) or placebo. The A-Study was conducted in North America (US and Canada). The B-Study was global, conducted in North America (US and Canada), Ireland, UK, South Africa, Australia and New Zealand.

[figure not shown]
Topline results from the STEADFAST A-Study failed to demonstrate a beneficial effect of azeliragon on the protocol specified primary endpoints. As a result, the ongoing studies (including the B-Study) were terminated, databases locked, and data analyzed. Although the STEADFAST A-Study and B-Study did not achieve statistical significance on either of the co-primary endpoints, important results were obtained through post-hoc subgroup analysis that warrant additional investigation.

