9.7.2 Statistical Methodology for Primary Analysis

The primary analysis will use the ITT methodology and a main-effects mixed-models for repeated measures (MMRM) methodology. The MMRM will utilize an unstructured covariance where the number of parameters is “ $t(t+1)/2$ ” where “ t ” is the dimension of the covariance matrix, using PROC MIXED in SAS. In the unlikely event of lack of convergence, Toeplitz structure will be employed where the number of parameters is “ t ” where “ t ” is the dimension of the covariance matrix. Time is considered as a class variable. Analysis will include treatment, time and treatment-by-time interaction as fixed effects, Baseline as covariate, and subject as a random effect. Supportive modeling will also include MMRM main-effects model with treatment, time, and subject.

Model assumptions will be evaluated. If the parametric assumptions are evaluated as inappropriate or violated, rank analogues will be advanced.

The primary analysis will be done for each stage separately. Part 1 will use alpha = 0.0499, which includes an adjustment of 0.0001 for interim analyses performed by the Independent Data Monitoring Committee (IDMC). The alpha adjustment for the IDMC for Part 1 is considered to be negligible, hence, the stated alpha for Part 1 is 0.05 for the 100-patient, 6-month trial. Part 2 will use alpha = 0.049, which includes an adjustment of 0.001 for interim analyses performed by the Independent Data Monitoring Committee (IDMC), thereby preserving the overall study-wise alpha = 0.05. The alpha adjustment of 0.001 is considered to be appropriate for the 200-patient, 18-month study.

Multiple imputations (MI) will be used as a supportive analysis with 100 invocations (acknowledging that more invocations are needed with more missing data). Monte Carlo methods are planned.

An essential component of the thorough analysis includes an assessment of the impact of missing data on study conclusions. As a part of assessing this impact, supportive analysis will include:

- an endpoint analysis (reduction to last-observation-carried-forward, justified in this study based on the monotonic progression of the natural course of AD and assuming no more dropouts in the group treated with azeliragon than in the group treated with placebo)
- a completers analysis (observed cases at endpoint)
- observed cases by assessment time.

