1.7 Early Stopping, Data Monitoring, and Interim Analysis

There will be no interim analyses.

An adjustment for alpha is included in the original protocol, as a conservative measure to accommodate unblinded evaluations by the independent data monitoring committee (IDMC). The alpha adjustment is applied to accommodate up to 10 analyses by the IDMC because the safety evaluation will include review of ADAS-Cog data from the safety perspective. Alpha = 0.0001 is apportioned to each of no more than 10 analyses by the IDMC that includes review of ADAS-Cog data.

There will be two database locks: one for the double-blind treatment period, and one for the follow-up period. Final analysis will be performed on the interim database after all subjects complete the treatment period (Month 6 or Early Termination) and all Treatment Period data is locked. The final database lock will occur after all Follow-up Visits are complete.

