1.10 Adaptive Study

This study is an adaptive trial, which includes 2 studies under the same protocol. This SAP is focused on Part 1 of this adaptive study.

This SAP conforms to standards set forth in *Adaptive Designs for Clinical Trials of Drugs and Biologics Guidance for Industry* (CDER, CBER, November 2019). The intention of the adaptive nature of this protocol is to leverage potential advantages related to statistical analysis as depicted in the FDA final guidance.

2 Statistical Hypotheses

Part 1 has a single primary endpoint (ADAS-Cog14).

The testing sequence will be as follows for strict significance, however proof of concept will be attained by significance in any of the outcomes below (Figure 1):

The first set of hypotheses to be tested is as follows:

H₀₁: The mean change in ADAS-cog14 in the active group is equal to that of the placebo group*.

H₁₁: The mean change in ADAS-cog14 in the active group is not equal (is superior) to that of the placebo group*.

Conditional on statistical significance, testing will proceed hierarchically:

H₀₂: The mean change in A-IADL in the active group is equal to that of the placebo group.

H₁₂: The mean change in A-IADL in the active group is not equal (is superior) to that of the placebo group[§].

Conditional on statistical significance, testing will proceed:

H₀₃: The mean change in CDR-sb in the active group is equal to that of the placebo group.

H₁₃: The mean change in CDR-sb in the active group is not equal (is superior) to that of the placebo group[§].

Conditional on statistical significance, testing will proceed:

H₀₄: The mean change in FAQ in the active group is equal to that of the placebo group.

H₁₄: The mean change in FAQ in the active group is not equal (is superior) to that of the placebo group[§].

H₀₅: The mean change in the cognitive composites or GST in the active group is equal to that of the placebo group.

H₁₅: The mean change in the cognitive composites or GST in the active group is not equal (is superior) to that of the placebo group.

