5.1.1 Primary Efficacy Variable

The primary analysis will include assessment of the following variables.

- Mean change from Baseline to Month 6 in ADAS-cog14*

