6.6 Statistical Methodology for Primary Efficacy Analysis

We will use $\alpha = 0.0499$, which includes an adjustment of 0.0001 for interim analyses performed by the Independent Data Monitoring Committee (IDMC).

In addition to the primary MMRM model, a last z-score carried forward (LZCF), will be run for the primary variable. Z-scores will be calculated for each timepoint. For individuals with missing data the last z-score will be carried forward. Let Z be the imputed z-score, while x is the last observation at timepoint t_1 and μ and σ are the mean and standard deviation of the next timepoint (t_2) for which the data is missing.

$$Z_{t2} = (x_{t1} - \mu_{t2}) / \sigma_{t2}$$

Z-scores imputed relative to the group mean and standard deviation at each timepoint, will better preserve the slope of each arm and thus is more robust to differences in dropout rate across treatment. The model using LZCF will be the primary analysis for the GST and the composite scores..

Descriptive summaries will be produced of the observed values and change from Baseline in ADAS-cog14 by treatment group at each individual time point and at endpoint (final on-treatment assessment for each subject).

For statistical analyses, 95% confidence intervals will be produced for the least-squares means (LSM) in each treatment group, as well as the LSM differences as compared to placebo. For MMRM and ANCOVA, two-sided p-values will be displayed for the comparison against placebo.

The primary analysis controls alpha through the conditional sequence of hypothesis testing. No further adjustment for multiplicity is necessary.

If the PPS differs from the FAS by more than 15%, the analyses will be replicated on the PPS. If the PPS and the FAS do not differ by more than 15%, analysis may not be done on the PPS. Final judgments will be made at the blind data review meeting in accordance with ICH E9.

6.6.1 PK

The trough PK concentration data collected prior to each dose will be used in a concentration response relationship analysis to assess correlation with each outcome which will mirror the primary analysis but replace the treatment variable with PK concentration.

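### The SAP 6.4 success rule is written for two studies with two primary endpoints at 0.049, but Part 1 is one study with one primary endpoint, and SAP 6.6 sets its alpha at 0.0499

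*SAP*

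**What the plan says.** SAP 6.4 (Adjustments for multiplicity) states when the study counts as statistically significant: when the "primary analysis has a resulting p-value less than 0.049 for both primary endpoints for both A-study and B-study".

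Other parts of the documents describe a different situation:

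- **Endpoint.** SAP Section 2 (Statistical Hypotheses) states "Part 1 has a single primary endpoint (ADAS-Cog14". SAP 5.1.1 lists one primary variable: "Mean change from Baseline to Month 6 in ADAS-cog14".
- **Scope.** SAP Section 1 and 1.10 limit the SAP to Part 1.
- **A-study and B-study.** Protocol 1.1.3 uses these names for the two STEADFAST trials run under TTP488-301: "Each study was independently powered to evaluate efficacy with respect to co-primary endpoints of ADAS cog11 and CDR-sb and were randomized separately". SAP 1.6 uses the names in the same way.
- **Alpha in the SAP.** SAP 6.6 sets 0.0499 for the primary analysis, "which includes an adjustment of 0.0001 for interim analyses performed by the Independent Data Monitoring Committee (IDMC". SAP 1.7 describes a different deduction: "Alpha = 0.0001 is apportioned to each of no more than 10 analyses by the IDMC that includes review of ADAS-Cog data". SAP 5.1.4 treats P > 0.05 on the ADAS-cog as not significant.
- **Alpha in the protocol.** Protocol 9.7.2 separates the parts: "Part 1 will use alpha = 0.0499, which includes an adjustment of 0.0001 for interim analyses", and "Part 2 will use alpha = 0.049, which includes an adjustment of 0.001 for interim analyses". It calls the Part 1 deduction negligible and gives the working alpha for Part 1 as 0.05. Protocol 9.14 spreads a total of 0.0001 over at most 4 IDMC analyses in Part 1, and allots 0.0001 to each of at most 10 in Part 2. Protocol 9.7.5 sets success at p < 0.05 on the primary analysis.
- **Precedence.** Protocol 9.0 and SAP 1.9 both say that the SAP supersedes the protocol's statistical section.

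**The concern.** Section 6.4 is the SAP's explicit statement of when the study has succeeded, and it refers to endpoints and studies that Part 1 does not have. It also sets a different threshold from the one that 6.6 sets for the same test.

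The hierarchy in SAP Section 2 moves to its next hypothesis only after a significant result, so what counts as significant must be fixed before unblinding. With 6.4 as it stands, someone would have to decide afterwards which clause to set aside and which of 0.049, 0.0499 or 0.05 applies. A p-value between 0.049 and 0.05 would miss the 6.4 threshold without meeting the numerical condition in 5.1.4 for moving to the composites and the global statistical test.

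**Working it through.** **Step 1: can the rule be applied?**

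| Element of SAP 6.4 | Part 1 (this SAP) | Part 2 (protocol) | STEADFAST (protocol 1.1.3) |
|---|---|---|---|
| Two primary endpoints | No: ADAS-cog14 only | Yes: ADAS-cog14 and CDR-sb | Yes: ADAS-cog11 and CDR-sb |
| An A-study and a B-study | No | No | Yes |
| Threshold 0.049 | No: 0.0499 | Yes | Not given |

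No part of TTP488-305 satisfies all three elements. Part 1, the only part this SAP covers, satisfies none.

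**Step 2: where the thresholds come from.**

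- SAP 1.7: 10 × 0.0001 = 0.001, and 0.05 − 0.001 = 0.049. This reproduces the 6.4 value, and it is the protocol's Part 2 scheme.
- SAP 6.6 and protocol 9.7.2 for Part 1: 0.05 − 0.0001 = 0.0499. This reproduces the 6.6 value.

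Both subtractions are correct. They use IDMC deductions that differ tenfold for one and the same test, so 1.7 and 6.4 stand together against 6.6.

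**Step 3: what the alpha gap is worth.** Inputs from SAP 1.6: N = 43, difference 1.54, SD 3.4, two-sided two-sample t-test. The SAP gives no arm sizes, so a 21/22 split is assumed.

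- SE = 3.4 × √(1/21 + 1/22) = 1.037
- Noncentrality = 1.54 / 1.037 = 1.485, with 41 degrees of freedom
- Smallest significant difference = critical t × SE; power from the noncentral t distribution

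| Alpha | Critical t | Smallest significant difference (points) | Power |
|---|---|---|---|
| 0.05 | 2.0195 | 2.095 | 30.53% |
| 0.0499 | 2.0205 | 2.096 | 30.50% |
| 0.049 | 2.0289 | 2.104 | 30.22% |

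The first row reproduces the 30% power stated in SAP 1.6. The chance that p falls between 0.049 and 0.05 is 0.05 − 0.049 = 0.001 under no effect, and 0.3053 − 0.3022 = 0.0031 under the assumed effect.

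At the originally planned 41 per arm (difference 2.9, SD 4), power is 90.0%, 90.0% and 89.9% at 0.05, 0.0499 and 0.049.

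**The case against.** The strongest reply is that this is leftover drafting with almost no practical effect. The intended test can be reconstructed from SAP Sections 2, 5.1.1 and 6.6. SAP 1.9 lists the changes from the protocol and names no new success rule. The hierarchy in Section 2 does not cite 6.4, and the proof-of-concept routes there do not run through it. As a threshold, 0.049 is the stricter value, so it cannot inflate type I error. All of this is fair, and it limits the weight of the point. It does not remove the contradiction: the sentence that defines success still cannot be applied.

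Four narrower points also stand:

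- The A/B labels belong to STEADFAST, but two primary endpoints at 0.049 would also fit Part 2. That the sentence was carried over from either source is an inference; that it does not fit Part 1 is not.
- The value 0.049 is traceable to SAP 1.7. What the documents lack is a reason to apply it to Part 1.
- The gap at 5.1.4 is not clear-cut. The footnote to Section 2 restates the trigger for the composites and the global test without a numerical cut-off, and Section 2 also allows an effect-size route to proof of concept.
- The figures in Step 3 come from a t-test without dropout, using ADAS-cog11 inputs. They size the alpha gap but do not describe the model in SAP 6.2.

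**Conclusion.** The concern holds. The rule in SAP 6.4 is wrong for Part 1 in its number of endpoints, its number of studies and its threshold, and the precedence given to the SAP means that protocol 9.7.5 does not correct it.

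The inapplicable rule is the substantive defect. The alpha mismatch costs about 0.3 percentage points of power at N = 43 and shifts the smallest significant difference by about 0.01 point. Those sizes rest on the assumed 21/22 split and the SAP 1.6 inputs. The contradiction itself rests on no assumption. It should be corrected before unblinding.

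**What to change.** Replace the sentence in SAP 6.4 with: *Part 1 demonstrates statistical significance if the two-sided p-value for the treatment difference in ADAS-cog14 change from Baseline to Month 6 in the primary analysis (Section 6.2) is below 0.0499.* Then:

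- State that the same threshold applies at each later step of the Section 2 hierarchy.
- In 5.1.4, define non-significance as p ≥ 0.0499.
- In 1.7, replace the 10-analysis scheme with a total of 0.0001 shared by at most 4 IDMC analyses, as protocol 9.14 sets out for Part 1.

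Using 0.05 throughout would also agree with the protocol, provided 6.6 is changed to match. What matters is a single threshold.

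The new sentence is only as definite as the primary analysis it points to. SAP 6.2 makes a mixed model primary, whereas SAP Section 7 describes multiple imputation as primary and MMRM as supportive. That is a separate matter and needs to be settled as well.

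The cost is SAP wording in 6.4, 5.1.4, 1.7 and the hierarchy statement in Section 2. Data collection and sample size are unaffected.

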6.5 Subgroup Analyses

6.5.1 Investigator Sites

Blind data review (recommended by ICH E9) may reveal many sites with few subjects randomized. Understanding the influence of site effects on analysis conclusions is essential and analyses to explore this are recommended in ICH E9 for key variables of analysis. A forest plot will be generated excluding each site one at a time to assess the impact of site for all efficacy measures.

6.5.2 Covariate and Categorical Interaction Analyses

The following variables will be assessed for interactions with the primary efficacy variable and time using the MMRM as described above:

- baseline score (for outcome being analyzed)
- baseline MMSE
- baseline HbA1C (continuous)
- ApoE4(carrier/non-carrier; discrete)
- ApoE4(number of E4 alleles; discrete)

6.6 Statistical Methodology for Primary Efficacy Analysis

We will use $\alpha = 0.0499$, which includes an adjustment of 0.0001 for interim analyses performed by the Independent Data Monitoring Committee (IDMC).

In addition to the primary MMRM model, a last z-score carried forward (LZCF), will be run for the primary variable. Z-scores will be calculated for each timepoint. For individuals with missing data the last z-score will be carried forward. Let Z be the imputed z-score, while x is the last observation at timepoint t_1 and μ and σ are the mean and standard deviation of the next timepoint (t_2) for which the data is missing.

$$Z_{t2} = (x_{t1} - \mu_{t2}) / \sigma_{t2}$$

Z-scores imputed relative to the group mean and standard deviation at each timepoint, will better preserve the slope of each arm and thus is more robust to differences in dropout rate across treatment. The model using LZCF will be the primary analysis for the GST and the composite scores..

Descriptive summaries will be produced of the observed values and change from Baseline in ADAS-cog14 by treatment group at each individual time point and at endpoint (final on-treatment assessment for each subject).

For statistical analyses, 95% confidence intervals will be produced for the least-squares means (LSM) in each treatment group, as well as the LSM differences as compared to placebo. For MMRM and ANCOVA, two-sided p-values will be displayed for the comparison against placebo.

The primary analysis controls alpha through the conditional sequence of hypothesis testing. No further adjustment for multiplicity is necessary.

If the PPS differs from the FAS by more than 15%, the analyses will be replicated on the PPS. If the PPS and the FAS do not differ by more than 15%, analysis may not be done on the PPS. Final judgments will be made at the blind data review meeting in accordance with ICH E9.

6.6.1 PK

The trough PK concentration data collected prior to each dose will be used in a concentration response relationship analysis to assess correlation with each outcome which will mirror the primary analysis but replace the treatment variable with PK concentration.

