* ADAS-Cog will also be run using LZCF. If neither of these are significant, the cognitive composites and global statistical test (GST) will be assessed for significance to demonstrate proof of concept. It is acknowledged that the present study is underpowered to replicate the clinically meaningful effect size observed in the STEADFAST combined A- and B-study diabetes subgroup. Therefore, if the observed effect size (treatment difference) or percent slowing (treatment difference divided by the placebo change) is equal to or greater than the corresponding values from the STEADFAST pooled analysis (-0.92; -61%), this will be considered proof of concept. Lack of strict statistical significance is expected with this range of effect size due to the small n, but this result, in the context of the consistency of the effect seen in STEADFAST Part A with the STEADFAST Part B data would provide proof of concept for this compound.

§ All secondary variables will also be run using LZCF.

3 Estimand Specification

This SAP is constructed to conform to regulatory guidance. In particular, this section is included as recommended by ICH E9 (R1) Addendum on estimands and sensitivity analysis in clinical trials to the guideline on statistical principles for clinical trials (30 August 2017).

In accordance with ICH E9 Addendum, the specification of the estimand is included in this SAP with the 4 attributes detailed in ICH E9 Addendum, Section A.3.1:

- A. The Population, that is, the subjects targeted by the scientific question:
For this study, the population consists of subjects with AD and HbA1c of 6.5% - 9.5% who meet eligibility requirements for the study, receive double-blind medication, and have at least one valid post-baseline measure of ADAS-cog(14).
- B. The variable (or endpoint) to be obtained for each patient, that is required to address the scientific question:
For this study, the primary endpoint is Change in ADAS-cog(14).
- C. The specification of how to account for intercurrent events to reflect the scientific question of interest:
Due to the small sample size intercurrent events will not be accounted for in this analysis.
- D. The population-level summary for the variable that provides, as required, a basis for a comparison between treatment conditions:
For this study, the population-level summary for the variable is the least-squares mean (LSM) of the treatment difference in mean change from baseline in ADAS-cog(14).

4 Populations of Analysis

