6.7 Statistical Methodology for Secondary Analysis

Secondary and exploratory endpoints that are measurement variables will use similar statistical methodology to the methodology used for primary analysis and will also use similar figures as those described in the associated TOC. Efficacy variables that are proportions will be analyzed using Mantel-Haenszel test. For the analysis of the categories for responders, a Cochran-Mantel-Haenszel test will be used.

Secondary endpoints will be performed using LZCF as described above. Composite and GST scores will only be run as LZCF.

Methodologies for variables that are categorical and summarized with proportions will include construction of confidence intervals for each treatment group and for the difference between groups. For analysis, Fisher’s exact test will be used for single-population analysis, and a Mantel-Haenszel test will be used for analyses combining data across strata.

Methodologies for time-to-event variables will include construction of 95% confidence intervals for each group separately and for the difference between groups. For analysis, a Wilcoxon test will be used for single-population analysis.

A graphical representation will be defined where the y-axis will show the cumulative percentage of subjects who achieved the specific measure of improvement or worsening in the ADAS-cog14 total score shown on the x-axis with a separate cumulative percentage curve for each treatment group.

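### SAP 6.6 leaves the LZCF reference group and modelled scale undefined, and its formula contradicts its wording; on the natural by-arm reading the treatment contrast is removed

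*SAP*

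**What the plan says.** SAP 6.6 adds LZCF to the primary MMRM. The rule in words is "Z-scores will be calculated for each timepoint" and then "For individuals with missing data the last z-score will be carried forward". The formula beneath it is Z_t2 = (x_t1 - mu_t2) / sigma_t2, where x_t1 is the last observation and mu_t2 and sigma_t2 are "the mean and standard deviation of the next timepoint". The stated benefit is that "Z-scores imputed relative to the group mean and standard deviation at each timepoint, will better preserve the slope of each arm". No step returns the result to points.

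LZCF is used widely:

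- SAP section 2, footnotes: "ADAS-Cog will also be run using LZCF" and "All secondary variables will also be run using LZCF".
- SAP 6.6: "The model using LZCF will be the primary analysis for the GST and the composite scores".
- SAP 6.7: "Composite and GST scores will only be run as LZCF".

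Other sections bear on scaling. SAP 5.1.5.6 and 8.1 standardise the GST to a screening/baseline mean taken over every patient. SAP 5.1.5.7 standardises the composite items within visit, across individuals. SAP 6.2 makes a risk-adjusted change score the model outcome, and there uses *group mean* for the mean of a treatment group.

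**The concern.** Three things that a programmer needs are missing or in conflict: whose mean and SD define the z-score, whether z-scores or points enter the model, and which z-score is carried.

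The natural reading of *group* is the treatment arm. SAP 6.2 uses the word that way, and the stated aim is to protect each arm's slope when dropout differs by treatment. Z-scores are to be calculated at every timepoint, not only where data are missing; the formula's output is a z-score; and the text then speaks of running the model. On that reading the analysis removes the difference that it is meant to estimate.

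The GST and composites are the fallback for proof of concept if ADAS-cog is not significant (SAP section 2 and 5.1.4), and ADAS-cog has only 30% stated power. SAP 1.6 credits the two composites with 49% and 47%. An unsettled rule therefore governs analyses on which the proof-of-concept conclusion may rest.

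**Working it through.** **1. The SAP's own figure.** Inputs from SAP 1.6: effect -1.54, SD 3.4, N = 43 (22/21 assumed), two-sided 0.05. SE = 3.4 × sqrt(1/22 + 1/21) = 1.037; t = 1.54 / 1.037 = 1.485 on 41 df; p = 0.145; power 30.5%. The SAP states 0.144 and 30%, so its figure reproduces. It states no figure for LZCF itself.

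**2. By-arm z-scores.** With z = (x - mean of the arm at that visit) / SD of the arm at that visit, the mean of z is 0 in each arm at each visit by construction. Illustration: azeliragon 26, 28, 30 (mean 28, SD 2) and placebo 30, 32, 34 (mean 32, SD 2) both become -1, 0, 1. A 4-point difference becomes 0.

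**3. Words against formula.**

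- Words: Z_t2 = Z_t1 = (x_t1 - mu_t1) / sigma_t1, which in points is x_t2 = mu_t2 + sigma_t2 × Z_t1.
- Formula: Z_t2 = (x_t1 - mu_t2) / sigma_t2, which in points is mu_t2 + sigma_t2 × Z_t2 = x_t1.

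The second is LOCF whatever the reference group. It freezes the dropout at the last score and preserves no slope.

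**4. Simulation.** 6000 trials, 22/21, visits at Baseline, Month 3 and Month 6, SAP effect and SD, t-test on Month 6 change. Assumed, because the documents do not give them: baseline mean 25 and SD 8, placebo decline 2.5, all dropout after Month 3. The 18% dropout is the planning value.

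With no dropout, by-arm z gives a difference of 0.000 and 0% rejection; pooled z gives -0.176 SD and 29.2%; points give -1.54 and 30.5%.

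With 18% dropout in each arm:

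| Implementation | Difference | Rejection, effect -1.54 | Rejection, no effect |
|---|---|---|---|
| By-arm z modelled, words | +0.002 SD | 4.0% | 4.3% |
| By-arm z modelled, formula | +0.019 SD | 11.6% | 10.7% |
| Pooled z modelled, words | -0.159 SD | 25.8% | 5.1% |
| Pooled z modelled, formula | -0.159 SD | 25.7% | 5.0% |
| By-arm, words, returned to points | -1.53 | 34.6% | 8.6% |
| Pooled, words, returned to points | -1.39 | 28.0% | 5.1% |
| Formula returned to points (LOCF) | -1.39 | 27.7% | 5.0% |

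**5. Range.** Placebo decline of 1.5 to 4 leaves the pattern unchanged: by-arm z +0.001 to +0.019 SD, pooled z -0.158 to -0.160 SD. With dropout of 10% on placebo and 26% on active, by-arm z gives about 0.000 SD. With that dropout and no true effect, by-arm carry-forward returned to points rejects 9.4%; LOCF shows a spurious -0.165 points, and pooled carry-forward by the words +0.033.

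**The case against.** The best defence is that the harmful reading defeats the plan's own purpose. It would flatten both slopes, which preserves nothing. SAP 6.6 asks for least-squares mean differences against placebo, and SAP section 2 defines percent slowing with the placebo change as divisor, which would be 0 with complete data. SAP 6.2 names a different model outcome, and the sentence on each arm's slope speaks of imputed scores, so LZCF can be read as a missing-data step only. For the GST and composites, SAP 5.1.5.6, 5.1.5.7 and 8.1 point to all-patient scaling, which keeps the contrast. The claimed benefit is also comparative: under the worded rule with pooled scaling, dropouts move with the visit mean, which is some gain over LOCF when dropout is unequal.

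Much of this stands. A reader might infer that the plan sets both arms' means to zero; the SAP never says that standardisation is within arm or that z-scores are the outcome, and even on that reading the zero is exact only with complete data. A reader might also infer that LZCF reverses the sign of the effect. With the SAP's effect the shift is about +0.02 SD, arises from the printed formula, and vanishes under the worded rule. Shifts of +0.04 to +0.05 SD appear only with the protocol's larger effect of 2.9 and with half the dropouts having no post-Baseline visit; the FAS requires a post-Baseline assessment.

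What does not stand is that the other sections settle the matter. The GST reference in SAP 8.1 is screening/baseline, whereas the mu and sigma in SAP 6.6 belong to the next visit. For ADAS-cog14, A-IADL, CDR-sb, FAQ and MMSE, no other section defines LZCF scaling.

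**Conclusion.** The point holds as a defect of specification with a serious consequence on one natural reading. It does not show that the planned model erases the effect.

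None of the readings examined makes the printed formula do what SAP 6.6 claims. By arm and modelled as z-scores, it removes the contrast and, at 18% dropout, roughly doubles false positives (10.7%). Returned to points, it is LOCF. With pooled scaling the contrast survives, but each arm's slope is not preserved.

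The by-arm zero with complete data and the LOCF identity are algebra and need no assumptions. The rejection rates rest on the assumed baseline distribution, placebo decline and dropout timing, and on a t-test in place of the SAP 6.2 model.

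The exposure is the LZCF runs of ADAS-cog14 and the secondaries, and the GST and composites if the pooled scaling is not applied to them. The primary ADAS-cog14 MMRM and the supportive multiple imputation are separate.

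**What to change.** Before unblinding, amend SAP 6.6 as follows.

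1. State that z-scores standardised within arm are never the modelled outcome.
2. Correct the formula to match the words, using all-patient visit means and SDs: carry z_t1, then set x_t2 = mean_t2 + SD_t2 × z_t1. Run the ADAS-cog14 and secondary models on points.
3. Scale the GST and composites, for observed and imputed records alike, by one all-patient baseline mean and SD. SAP 5.1.5.6 and 8.1 already do this for the GST; SAP 1.6 describes a baseline reference for the composite, but 5.1.5.7 uses the visit and should be aligned. Impute before scaling: with a fixed reference, z_t2 = z_t1 implies x_t2 = x_t1, which is LOCF again.
4. If arm-specific imputation is wanted, use multiple imputation so that its uncertainty is counted. Adding a back-transformation to single by-arm carry-forward is not enough, since it rejected about 8% to 9% with no true effect.
5. Drop the claim that each arm's slope is preserved.

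The cost is a few sentences and some programming, with no new data. The statistical price is that dropouts follow the common visit mean, which drew the simulated effect from -1.54 to -1.39 points at 18% dropout.
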